6.7. Compliance with Study Treatment Administration

Subjects are dosed at the site, and will receive study treatment directly from the Investigator or designee, under medical supervision. The date and time of each dose administered in the clinic will be recorded in the source documents. The dose of study treatment and study subject identification will be confirmed at the time of dosing by a member of the study site staff other than the person administering the study treatment.

6.8. Treatment of Study Treatment Overdose

In the event of an overdose the Investigator should:

1. contact the Medical Monitor immediately
2. closely monitor the subject for adverse events (AEs)/serious adverse events (SAEs) and laboratory abnormalities until albiglutide or exenatide can no longer be detected systemically (at least 25 days for albiglutide or 24 hrs for exenatide).
3. document the quantity of the excess dose as well as the duration of the overdosing in the eCRF.

6.8.1. Albiglutide

For this study, once the 50 mg dose of albiglutide is administered, any dose of albiglutide administered after that will be considered an overdose.

No data are available with regard to albiglutide overdose in humans. The highest recommended dose of albiglutide is 50 mg once weekly. During clinical studies of subjects with T2DM, the highest dose of albiglutide administered was 100 mg subcutaneously every 4 weeks for 12 weeks. This dose was associated with an increased frequency of nausea, vomiting, and headache. There is no specific antidote for overdose with albiglutide. In the event of a suspected overdose, the appropriate supportive clinical care should be instituted, as dictated by the subject's clinical status. Anticipated symptoms of an overdose may be severe nausea, vomiting, or headache. A prolonged period of observation and treatment for these symptoms may be necessary, taking into account the half-life of albiglutide (5 days).

6.8.2. Exenatide (Byetta)

Overdosage of exenatide is described in the latest Byetta product insert [[BYETTA](#) for injection, AstraZeneca 2015] as follows:

“In a clinical study of Byetta, three patients with type 2 diabetes each experienced a single overdose of 100 mcg SC (10 times the maximum recommended dose). Effects of the overdoses included severe nausea, severe vomiting, and rapidly declining blood glucose concentrations. One of the three patients experienced severe hypoglycemia requiring parenteral glucose administration. The three patients recovered without complication. In the event of overdose, appropriate supportive treatment should be initiated according to the patient's clinical signs and symptoms.”

6.9. Treatment after the End of the Study

Subjects will not receive any additional treatment from GSK after completion of the study because only healthy volunteers are eligible for study participation.

6.10. Lifestyle and/or Dietary Restrictions

6.10.1. Meals and Dietary Restrictions

Subjects must refrain from eating and drinking anything but water starting at approximately 10 pm the night before or within 8 hours of the start of their MRI appointment until completion of all study assessments on imaging day. Subjects can drink water, but no more than 8 oz at a time and not within 2 hours of the appointment.

The subjects will be offered a small meal prior to leaving the site after each post-dose scanning session visit.

6.10.2. Caffeine, Alcohol, and Tobacco

- Subjects will abstain from ingesting caffeine- or xanthine-containing products (e.g., coffee, tea, cola drinks and chocolate) after 10 pm the evening prior to each MRI session day until completion of all study assessments on imaging day during each session.
- Subjects will abstain from alcohol for 24 hours prior to each dosing and each MRI session day until completion of all study assessments on imaging day during each session.
- Use of tobacco products is not allowed from 3 months prior to screening until after the final follow-up visit.

6.11. Concomitant Medications and Non-Drug Therapies

6.11.1. Prohibited Medications and Non-Drug Therapies

Subjects must abstain from taking prescription (excluding oral contraception) or non-prescription drugs (including vitamins and dietary or herbal supplements) during the study, unless in the opinion of the Investigator and Medical Monitor, the medication will not interfere with the study.

Any subject requiring medications that

- may produce or reduce nausea or significantly affect gastrointestinal motility such as prokinetics (e.g., erythromycin), anti-emetics (e.g., metoclopramide), narcotic analgesics (e.g., morphine), anticholinergics (e.g., domperidone), anti-acids (e.g., pump inhibitors, H2 blockers), laxatives and drugs affecting pancreatic or hepatobiliary systems, or
- may stimulate or inhibit CNS (e.g., modafinil, dexamphetamine, methylphenidate, bromopheniramine, chlorpheniramine, clemastine, diphenhydramine, hydroxyzine)

may be withdrawn from the study at the discretion of the Investigator based on the reason (i.e., AE), duration of exposure and relative to the timing of the scans in consultation with the Medical Monitor.

7. STUDY ASSESSMENTS AND PROCEDURES

Protocol waivers or exemptions are not allowed with the exception of immediate safety concerns. Therefore, adherence to the study design requirements, including those specified in the Time and Events Table, are essential and required for study conduct.

This section lists the procedures and parameters of each planned study assessment. The exact timing of each assessment is listed in the Time and Events Table Section [7.1](#).

Procedure	Screening	Session 1											Wash out	Session 2						F/U
	Week -4 to -1	Day 1			Day 5±1 ^m	Day 8±1 ^m					Post MRI	6-9 weeks	Day 1	Day 4±1 ^m					Week 13	
		Pre-MRI	MRI	Post MRI		-2 h	-0.5 h	0 h	0.5 h	1 h				0.5 h	1 h	-2 h	-0.5 h	0 h		0.5 h
Randomization	X																			
Dosing albiglutide or placebo ^g					X							X								
Dosing exenatide or placebo ^g							X							X						
MRI ^h		X							X							X				
Autonomic monitoring		X							X							X				
Electrogastrogram		X							X							X				
VAS		X		X				X		X				X		X				
MSAQ ⁱ				X						X							X			
Capillary blood glucose										X							X			
Fasting Plasma Glucose										X							X			
Snack ^j				X						X							X			
AE assessment ^k		<----->			<----->							<----->					X			
Discharge ^l				X						X							X			

- a. Medical history includes alcohol/tobacco/caffeine usage.
- b. Prior-Medications are defined as prescription or over-the counter medications taken within 30 days of Screening. Record concomitant medications and or changes.
- c. WCBP is women of child-bearing potential. Serum pregnancy test at Screening. Urine pregnancy at other specified time points.
- d. If test otherwise performed within 1 month prior to first dose of study treatment, testing at screening is not required.
- e. See Table 2 for list of laboratory parameters. Unscheduled Safety Labs and ECGs can be done at any time if the Investigator considers the assessments appropriate for subject safety.
- f. Mock fMRI is performed on a separate day during the screening period. Scheduling should allow at least 1 week between the Mock fMRI and the next MRI scan.
- g. Albiglutide, exenatide or placebo is administered according to randomization sequence.
- h. All MRI include resting-state fMRI, ASL and MRS. Off-therapy MRI scan includes visual nauseogenic task fMRI and can be initiated once -assessments are completed. The on-therapy scan should be initiated 1 hr ±15min post the exenatide or exenatide placebo dose. Pre-scan procedure timings are suggested times to allow completion of activities. Post MRI procedure should be completed at the noted times ±15 min.

- i. MSAQ is given following the VAS.
- j. Subjects will be offered a snack prior to leaving the site.
- k. Only events related to the Study Procedures meeting the SAE criteria are reported after screening and before dose on Session 1 Day 5.
- l. Subjects should remain at the site for at least 1 hr after completion of MRI. All procedures and assessments must be complete prior to discharge. The Investigator will approve the release of the subject from the clinic, or will provide treatment for the standard of care as required.
- m. The Post-dose MRI **MUST** be scheduled 4 ± 1 days after the albiglutide or albiglutide placebo dose. The day of dosing albiglutide is counted as the first day.

Procedure	Screening		Session 1						Wash out	Session 2						F/U							
	Week -4 to -1		Day 1	Day 4±1 ^m					6-9 weeks	Day 1			Day 5±1 ^m	Day 8±1 ^m					Week 13				
	1	2		-2h	-0.5h	0h	0.5h	1h		Post MRI	Pre-MRI	MRI		Post MRI	0.5h	1h	-2h	-0.5h		0h	0.5h	1h	Post MRI
Visit (all out-patient)	1	2	3	4							5			6	7					8			
Dosing albiglutide or placebo ^g			X									X											
Dosing exenatide or placebo ^g					X											X							
MRI ^h								X			X								X				
Autonomic monitoring								X			X								X				
Electrogastrogram								X			X								X				
VAS						X		X			X	X				X			X				
MSAQ ⁱ								X			X								X				
Capillary blood glucose								X											X				
Fasting Plasma Glucose								X											X				
Snack ^j								X			X								X				
AE assessment ^k			X	←-----→							←-----→			X	←-----→					X			
Discharge ^l								X				X							X				X

- a. Medical history includes alcohol/tobacco/caffeine usage.
- b. Prior-Medications are defined as prescription or over-the counter medications taken within 30 days of Screening. Record concomitant medications and or changes
- c. WCBP is women of child-bearing potential. Serum pregnancy test at Screening. Urine pregnancy at other specified time points
- d. If test otherwise performed within 1 month prior to first dose of study treatment, testing at screening is not required
- e. See Table 2 for list of laboratory parameters. Unscheduled Safety Labs and ECGs can be done at any time if the Investigator considers the assessments appropriate for subject safety. The blood sample Session 2 Day 5 must be collected prior to dosing.
- f. Mock fMRI session is performed on a separate day during the screening period. Scheduling should allow at least 1 week between the Mock fMRI and the next MRI scan.
- g. Albiglutide, exenatide or placebo is administered according to randomization sequence.

- h. All MRI include resting-state fMRI, ASL and MRS. Off-therapy MRI scan includes visual nauseogenic task fMRI and can be initiated once -assessments are completed. The on-therapy scan should be initiated 1 hr \pm 15min post the exenatide or exenatide placebo dose. Pre-scan procedure timings are suggested times to allow completion of activities. Post MRI procedure should be completed at the noted times \pm 15 min.
- i. MSAQ is given following the VAS.
- j. Subjects will be offered a snack prior to leaving the site.
- k. Only events related to the Study Procedures meeting the SAE criteria are to be reported after screening and before dose on Session 1 Day 1.
- l. Subjects should remain at the site for at least 1 hr after completion of MRI. All procedures and assessments must be complete prior to discharge. The Investigator will approve the release of the subject from the clinic, or will provide treatment for the standard of care as required.
- m. The Post-dose MRI **MUST** be scheduled 4 \pm 1 days after the albiglutide or albiglutide placebo dose. The day of dosing albiglutide is counted as the first day.

7.2. Screening and Critical Baseline Assessments

The following demographic parameters will be captured: year of birth, gender, race and ethnicity.

Medical/medication/family history will be assessed as related to the inclusion/exclusion criteria listed in Section 5.

7.2.1. Motion Sickness Susceptibility Questionnaire Short (MSSQ-Short)

The MSSQ-Short will be completed by each potential subject at the screening visit. The questionnaire collects brief background information and consists of two sections [Appendix 6]. Section A collects the subject's childhood experience (before age 12) with travel and motion sickness. Section B collects the subjects experience of travel and motion sickness over the last 10 years [Golding, 2006].

7.2.2. Edinburgh Handedness Inventory

The Edinburgh Handedness Inventory consists of 10 items summarized as follows: (1) writing, (2) drawing, (3) throwing, (4) scissors, (5) toothbrush, (6) knife, without fork, (7) spoon, (8) broom (upper hand), (9) striking a match (match), and (10) opening box (lid). Respondents are required to indicate their hand preference and strength of preference [Appendix 5].

7.2.3. Mock fMRI

Subjects will be oriented to the visual motion sickness stimulus, while inside of a mock fMRI scanner (a plywood constructed replica). The subject will practice rating nausea severity and get comfortable with the scale, as well as their own limits with respect to severe nausea on the verge of vomiting. This will improve safety when they are then experiencing similar sensations inside the fMRI magnet.

The visual motion stimulation will be projected onto a screen with a field-of-view approximately 150°. This large unimpeded field of view is critical for inducing motion sickness with visual stimuli. A concave screen will be positioned 10 cm in front of their eyes, onto which visual stimuli will be projected, from behind. The nauseogenic stimulus will be a standardized visual presentation of alternating black (1.2 cm, 6.9° viewing angle) and white (1.85 cm, 10.6° viewing angle) stripes with left-to-right motion at ~62.5°/s. This left-to-right horizontal translation induces a vection sensation wherein subjects experience a false sensation of translating to the left. Such images simulate the visual input provided by a rotating optokinetic drum, commonly used to induce vection (illusory self-motion) and nausea. Symptoms severity will be rated as described below. Following the procedure, study personnel will debrief the subjects to ensure that they understand the rating levels and procedure.

0= no nausea, 1= minimal nausea, 2= mild nausea, 3= moderate nausea, 4= severe nausea

7.3. Endpoints

7.3.1. Magnetic Resonance Imaging

All MRI assessments will be acquired on a Siemens 3T system located at the Martinos Center for Biomedical Imaging. All Martinos scanners undergo quality assurance (QA) assessments every morning to ensure that fMRI signal drifts and variances are within limits and that signal spiking is not occurring.

Imaging scans will be reviewed by trained technologists and abnormal findings will be consulted with a radiologist. Subjects will be advised to seek consultation based on the radiologist's opinion.

Structural MRI:

Structural MRI data will be collected prior to all fMRI and MRS data collection using a T1-weighted magnetization-prepared rapid gradient-echo (MP-RAGE) pulse sequence. These data will be used to help align functional data to the MNI space, while exploratory analysis of gray matter volume and cortical thickness can be related to functional brain response and symptom severity.

Functional MRI

All fMRI analyses will use a combination of tools, previously validated, and used in the [name] Lab for the analysis of similar data. Tool packages will include: FSL (FMRIB Software Library; <http://www.fsl.fmrib.ox.ac.uk/fsl/>), AFNI (Analysis of Functional NeuroImages; <http://afni.nimh.nih.gov/afni>), and FreeSurfer (<http://surfer.nmr.mgh.harvard.edu/>).

BOLD fMRI Resting

Resting functional connectivity will be assessed using data acquired in the first 6 minutes of the vection task scan run, i.e. when the subject is resting, before any motion sickness provocation during the Off-therapy scan. For on-drug MRI visits, a separate 6-minute BOLD fMRI resting state scan will be performed, and subjects will verbally rate (0-100 NRS) their nausea intensity before and after this scan. Data will be analysed using validated independent component analysis (ICA) methods and seed voxel connectivity methods using functional localizer seeds obtained from the results of the motion sickness fMRI analyses.

BOLD fMRI Visual Nauseogenic Task

The 3T MRI will include a specially configured, open-design multichannel head coil. For the visual nauseogenic task BOLD fMRI scan run, subjects will lay supine inside the MRI scanner while visual stimuli are projected onto a screen encompassing their entire field of view. Subjects will be instructed to remain as still as possible, focus directly on the stimulus, and maintain as constant a rate of breathing as possible (i.e. not perform any respiratory maneuvers to decrease nausea). Subjects will be instructed to keep their eyes open and just let the nausea sensation evolve. The fMRI scan run will consist of a visual

fixation baseline for 6 min, followed by a visual presentation of alternating black/white stripes translating to the subjects' right field of view (gray background). Nausea produced by the visualvection signal will be rated using a button box. Once subjects rate a nausea level 4 (severe nausea) or 20 mins has passed, the stripes stimulation will be terminated and subjects will cross-hair fixate again for 6 min.

Arterial spin labeling (ASL)

ASL will be used to assess resting regional Cerebral Blood Flow (rCBF). The pseudo-Continuous ASL (pCASL) method will be used, which allows for adequate signal with whole brain coverage. rCBF maps will be contrasted, comparing flow maps under different drug conditions, and in comparison with a non-drug resting state (data collected during the off-therapy MRI visit, before thevection nausea task). Serial tagged and untagged image volumes will be subtracted, and the difference metric will be used in conjunction with an assumed T1 of gray matter tissue, partition coefficient, efficiency, and established equations for estimating rCBF.

Magnetic Resonance Spectroscopy (MRS) (GABA and glutamate)

GABA and glutamate magnetic resonance spectroscopy will be measured at rest. It will be measured prior to the motion sickness fMRI task run during the off-therapy scan. A newly developed motion-corrected 3D MRS sequence that reliably edits GABA and glutamate will be used for non-invasive brain mapping of neurotransmitter concentration. The field of view will cover key nausea processing areas such as insula, cingulate, and basal ganglia. The study will use a newly developed motion-corrected 3D magnetic resonance spectroscopy imaging (MRSI) sequence that, reliably evaluates glutamate/glutamine (GLX) concentration (FOV = 200x200x200, matrix=10x10x10, voxel 8 cc). Spectra will be fitted with LCModel and metabolic maps will be obtained from the fitted signals. The neurochemical maps will be transformed from anatomical subject space to MNI 152 standard space using non-linear registration (FNIRT, FSL). A novel group level analysis of spectroscopic data will be performed using a mixed effects model in the MNI152 standard space to detect significant regional changes of neurotransmitter levels under different drug and non-drug conditions.

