5.1. Inclusion Criteria

A subject will be eligible for inclusion in this study only if all of the following criteria apply:

AGE
1. Between 18 and 50 years of age inclusive, at the time of signing the informed consent.

TYPE OF SUBJECT AND DIAGNOSIS INCLUDING DISEASE SEVERITY
2. Healthy as determined by the Investigator or medically qualified designee based on a medical evaluation including medical history, physical examination, laboratory tests and cardiac monitoring.
3. Pure right-handed based on Edinburgh Handedness Inventory (Appendix 5)
4. Motion Sickness Susceptibility Questionnaire (MSSQ-short) Screening score >17 and mock fMRI nausea rating ≥ 2 (See Appendix 6)
5. A subject with a clinical abnormality or laboratory parameter(s) which is/are not specifically listed in the inclusion or exclusion criteria, outside the reference range for the population being studied may be included only if the Investigator (in consultation with the Medical Monitor, if necessary) decides and documents that the finding is unlikely to introduce additional risk factors and will not interfere with the study procedures or ability to interpret study results.

WEIGHT
6. Subject's body mass index (BMI) is $\geq 19 \text{ kg/m}^2$ and $\leq 30 \text{ kg/m}^2$.

SEX

7. Male OR
8. Female: eligible to participate if she is not pregnant (as confirmed by a negative human chorionic gonadotrophin (hCG) test at screening and at other timepoints), not lactating, and at least one of the following conditions applies:
 - Non-reproductive potential defined as:
 - Pre-menopausal females with one of the following:
 - Documented tubal ligation
 - Documented hysteroscopic tubal occlusion procedure with follow-up confirmation of bilateral tubal occlusion
 - Hysterectomy
 - Documented Bilateral Oophorectomy
 - Postmenopausal defined as 12 months of spontaneous amenorrhea [in questionable cases a blood sample with simultaneous follicle stimulating hormone (FSH) and estradiol levels consistent with menopause to confirm (refer to laboratory reference ranges for confirmatory levels)].
 - Reproductive potential and agrees to follow one of the options listed below in the GSK Modified List of Highly Effective Methods for Avoiding Pregnancy in Females of Reproductive Potential (FRP) requirements from 30 days prior to the first dose of study medication and for the duration of study including the completion of the follow-up visit.

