11. ATTACHMENTS [DOCUMENTATION FROM MARTINOS]

11.1. Reporting & Analysis Plan for Imaging Data for Part A

11.1.1. Overview of Quality Control for Imaging Data

Quality control procedures will include visual inspection of raw brain images for presence of various artifacts, including but not limited to, aliasing, excessive distortion, Nyquist N/2 ghosting, and signal inhomogeneities. We will also assess head motion correction parameters to ensure that subjects were not moving excessively during the functional MRI (BOLD fMRI and pCASL) scans. We will evaluate 1) total translation and rotation motion, 2) relative TR-to-TR motion, 3) number of relative translations (> 0.1 mm). For pCASL data, we will calculate rCBF and ensure values within the gray matter are within normal bounds (40-60 mm/100 g tissue/min). For ¹H-MRS data we will assess spectra to ensure adequate SNR (Cramer–Rao lower bounds values below 40%).

We will perform single-subject level analyses and include data from (1) resting-state BOLD fMRI, (2) pseudo-continuous arterial spin labelling (pCASL), and (3) proton-density weighted magnetic resonance spectroscopy (¹H-MRS).

Primary Outcomes/Endpoints:

1. Resting-state functional connectivity (resting-state BOLD fMRI)
2. Regional cerebral blood flow (rCBF) (pCASL)
3. Glutamine/Glutamate (Glx) and GABA concentrations (¹H-MRS)

1. Resting-state fMRI (rs-fMRI)

Resting-state BOLD signal MRI data collected at off-therapy and exenatide post-dose MRI scan sessions will be analyzed using a whole-brain seed-to-voxel approach. The seed-to-voxel driven approach will include *a priori* seed ROIs placed in brain areas subserving nausea-related processing including regions identified from our prior study ([name] et al. Cereb Ctx 2013). These regions will include: interoceptive/sensory (insula, dACC), emotional/affective (amygdala, pgACC), and cognitive/evaluative (dlPFC/OFC) brain areas, primary visual (V1) and extrastriate cortices (area MT+/V5). Group analyses will be performed using a paired t-test (off-therapy vs. exenatide) with FSL's FLAME (FMRIB's Local Analysis of Mixed Effects).

2. pCASL

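### Off-therapy resting BOLD is taken from inside the vection task run and on-drug resting BOLD from a separate run, so the exploratory drug-versus-off connectivity contrasts cannot be assigned to drug alone

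*Protocol*

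**What the plan says.** Resting-state BOLD is one of the primary endpoints (Protocol 3; SAP 2.2). Protocol 7.3.1 obtains it in two ways:

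- **Off-therapy visit:** "Resting functional connectivity will be assessed using data acquired in the first 6 minutes of the vection task scan run". The task description in the same section shows what that segment is: a visual "fixation baseline for 6 min, followed by a visual presentation of alternating black/white stripes". For the task run, "Subjects will be instructed to keep their eyes open and just let the nausea sensation evolve".
- **Drug visits:** "For on-drug MRI visits, a separate 6-minute BOLD fMRI resting state scan will be performed". A spoken nausea score from 0 to 100 is taken on either side of this run. No display or eye instruction is given for it.

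The vection task takes place at the off-therapy visit only (Protocol 9.3). That visit has no injection of any kind (Protocol 4.1), whereas both drug-day scans follow an exenatide or saline injection.

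Protocol 9.3 lists drug-versus-off differences among the main BOLD contrasts, and Protocol 9.4 tests them in an ANOVA with treatment and period fixed and subject random. The SAP attachment (11.1.1) analyses "Resting-state BOLD signal MRI data collected at off-therapy and exenatide post-dose MRI scan sessions" and names a paired t-test between the two. SAP 2.1, however, records a decision not to complete group analysis of the four Part A subjects.

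**The concern.** A drug-versus-off contrast is informative about drug only if the two scans differ in drug and in nothing else that matters. Here they also differ in how rest was acquired: one is the lead-in to a nauseogenic stimulus within a single run, the other a free-standing run bracketed by nausea ratings. A difference in connectivity could appear with no drug effect at all.

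The SAP attachment places its seeds in the insula, cingulate, amygdala, prefrontal cortex, V1 and MT+/V5. A change of visual display or mental state could plausibly move connectivity in several of these.

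There is also a plausible route through anticipation. Before any real scan, "Subjects will be oriented to the visual motion sickness stimulus, while inside of a mock fMRI scanner", and entry requires a "mock fMRI nausea rating ≥ 2" (Protocol 5.1). Subjects in the off-therapy fixation period thus know the stimulus and have felt nauseated by it.

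At stake is the reading of the off-therapy versus exenatide resting-connectivity comparison, the only imaging group comparison that the SAP specifies.

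**Working it through.** The plan gives no figure to reproduce: no alpha, power, effect size or SD is stated for this endpoint, and Protocol 9.1 sets no hypothesis. The question is whether run type can be separated from drug.

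**Step 1. Layout (Protocol 4.2, Table 1, with 7.3.1).** Each subject has three resting acquisitions.

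| Scan | Run type | Injection before scan | Vection task follows |
|---|---|---|---|
| Off-therapy | inside task run | none | yes |
| Albiglutide | stand-alone | yes (saline that day) | no |
| Exenatide | stand-alone | yes | no |

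This holds in all four sequences. Randomizing the session of the off-therapy scan changes its order but not its run type.

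**Step 2. Algebra.** Let A and E be indicators for the albiglutide and exenatide scans, and R the indicator for the embedded run. In every row R = 1 − A − E. The subject columns sum to 1, so R is an exact linear combination of columns already in the Protocol 9.4 model.

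**Step 3. Rank check.** The columns are N subjects, period, A, E and R, that is N + 4. Allocation to the four sequences is equal.

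| N | Columns with R | Rank with R | Rank without R |
|---|---|---|---|
| 4 (Part A as completed) | 8 | 7 | 7 |
| 24 (planned) | 28 | 27 | 27 |
| 28 (planned, with second Part A cohort) | 32 | 31 | 31 |

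Adding R never raises the rank. Run type cannot be estimated at any sample size.

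**Step 4. Bias.** With zero drug effect and a run-type effect of +1 on off-therapy scans, fitting the model without R gives:

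- albiglutide − off = −1.0
- exenatide − off = −1.0
- albiglutide − exenatide = −1.0 − (−1.0) = 0.0

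The paired t-test in the SAP attachment estimates exenatide − off directly and carries the same −1.0.

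**Step 5. The same check with one run type at all scans.** R is then constant, and the run-type bias in both drug-minus-off contrasts falls from 1.0 to 0 in size. The injection indicator equals A + E = 1 − R under the present layout, and it stays aliased after run type is matched. So does the fact that the vection task is still to come at that visit.

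**Step 6. Illustration only.** Take a two-sided 0.05 paired t-test on one connectivity measure, zero drug effect, and an assumed run-type shift of δ SDs of the paired difference. The rejection rate is P(|T| > t) with T noncentral t on N − 1 df and noncentrality δ√N. For example, N = 24 and δ = 0.3 give noncentrality 0.3 × √24 = 1.47 and a rate of 0.29.

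| Assumed δ | N = 4 | N = 24 | N = 28 |
|---|---|---|---|
| 0 | 0.05 | 0.05 | 0.05 |
| 0.2 | 0.06 | 0.16 | 0.18 |
| 0.3 | 0.07 | 0.29 | 0.33 |
| 0.5 | 0.11 | 0.65 | 0.72 |
| 0.8 | 0.21 | 0.96 | 0.98 |

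The documents give no value for δ, so the table shows sensitivity and does not estimate the error rate of this trial.

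**Step 7. Choice of off-therapy data point.** Protocol 9.3 writes the BOLD drug-versus-off contrasts against DP2, the task, although its own table puts resting BOLD at DP1. Read literally, that compares drug-day rest with the task itself. Reading DP1 instead leaves the run-type difference described here.

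**The case against.** Several points on the other side have force.

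- **The primary comparison is clean.** A reader might infer that the primary resting-BOLD result as a whole is compromised. It is not: the primary objective compares albiglutide with exenatide, both use the stand-alone run, and Step 4 gives zero bias. This stands.
- **Anticipation is not documented.** A reader might infer that anticipated nausea is a known confounder here. No section measures or states it. Nor is expectation confined to the off-therapy day: on drug days subjects have been told of gastrointestinal risks through consent (Protocol 4.6.1), have had a blindfolded injection (6.4), and rate nausea before the run. Its net direction and size are unknown. This stands.
- **Display and instructions are not shown to differ.** The protocol is silent on them for the on-drug run, and it does not say that ratings are absent around the off-therapy segment. Duration is the same, 6 minutes. What is documented is embedded versus stand-alone, with ratings described for drug days only. This stands, but it is also a reason to specify them.
- **Matching the run would not make the contrast a pure drug effect.** Off-therapy has no injection, and the task still follows later in that visit. This stands, and limits what the fix can claim.
- **Part A existed to test scanning paradigms before Part B (Protocol 4.1), and the study is exploratory.** That offered a route to revise the run, but not a commitment to do so. Exploratory status lowers the stakes without separating run type from drug.
- **Group analysis may not happen.** SAP 2.1 says it will not be completed, while the attachment announces single-subject analyses and also a paired group test. The aliasing affects a single-subject off-versus-exenatide comparison just as much.

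None of this removes the documented difference in run type or makes it estimable.

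**Conclusion.** The point holds for the drug-versus-off contrasts only. Run type is fully aliased with off-therapy versus drug in every subject, any run-type effect enters those contrasts in full, and neither the ANOVA nor the paired t-test can remove it. The absence of an injection at the off-therapy visit is a second difference aliased in the same way. An off-therapy versus exenatide or off-therapy versus albiglutide difference in resting connectivity therefore cannot be attributed to drug alone.

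The conclusion about aliasing rests on the acquisition text in Protocol 7.3.1 and the four sequences, and needs no assumption about size. The size of the bias cannot be derived from the documents; the rejection rates above depend wholly on assumed shifts and, at the four subjects actually completed, run from 0.06 to 0.21 over the shifts tried. This is an inexpensive design improvement and a limit on interpretation. It does not show that a run-type effect or an anticipation effect exists.

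**What to change.** **In the design, or if the design is reused.** Acquire the same stand-alone 6-minute resting run at all three scans, with the same display, eye instruction, nausea ratings and slot in the session. On the off-therapy day place it before the vection run, and use it as DP1 in Protocol 9.3. The cost is about 6 minutes of scanner time at one of three scans. At minimum, give the on-drug run the same fixation display and instructions as the task baseline, and write them into Protocol 7.3.1; this adds no scanner time. The full version removes the run-type difference. Neither version removes anticipation of the task or the no-injection difference, and both should be stated as remaining limits.

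**For the completed Part A data.** Acquisition can no longer change. State in the SAP and the report that off-therapy versus exenatide differences in resting connectivity, at single-subject or group level, cannot be attributed to exenatide alone, and name run type and the missing injection as the reasons. Reconcile SAP 2.1, which drops group analysis, with the paired t-test in SAP 11.1.1. The cost is a few sentences.
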